7.8.1.4 AEs of special interest (AESI)

The protocol defines the following adverse events that for analysis purposes will be considered as AESIs:

- Decreased renal function
- Hepatic injury
- Diabetic ketoacidosis (DKA)
- Events leading to lower limb amputation

Events of these AESIs are identified through the AE being flagged by the investigator as an AESI on the CRF.

AE frequency tables will be created for renal and hepatic events based on narrow SMQs.

Renal: 20000003 Acute renal failure

Hepatic: 20000008 Liver related investigations, signs and symptoms (SMQ)

20000009 Cholestasis and jaundice of hepatic origin (SMQ)

20000010 Hepatitis, non-infectious (SMQ)

20000013 Hepatic failure, fibrosis and cirrhosis and other liver damage-related conditions

The frequency of patients with DKA will be summarised based on the applicable BIcMQ at the time of the analysis.

The frequency of patients with events leading to lower limb amputation will be summarised.

In addition, muscle weakness will be tabulated by treatment group, which will be defined by the PTs of Sarcopenia, Muscular weakness, Muscle atrophy, Muscle fatigue and Myopathy.

7.8.1.5 Events qualifying for external adjudication by the Clinical Event Committee (CEC)

An independent external CEC regularly reviews events and evaluates whether pre-specified criteria for these adjudication endpoints are met. Details on composition of the CEC, responsibilities and clinical event definitions are provided in a separate CEC Charter.

The CEC will be provided with additional, specified background material on the patients with these events and perform an assessment of the events.

Adjudication assessments will be incorporated to the database. Frequency tables will be provided for the PTs in the specified SMQs of events and for the adjudication endpoints. Tables will be provided for events qualifying for adjudication and then separately the events that were confirmed or non-assessable.

7.8.1.6 Analysis of adjudicated events

DKA and hepatic events will be adjudicated by an external expert committee. The patients with adjudicated hepatic events will be summarized.

7.8.1.7 AEs while patients taking wrong medication

A listing will be provided for AEs that occurred while a patient was taking the wrong medication. If such a patient is identified, an additional adverse event table that assigns the adverse events to the actual treatment taken will be presented. A patient who took both the assigned treatment and at least one tablet of the wrong treatment, will be counted as at risk in both treatment groups for the respective relevant time. The table will include all adverse events by SOC and PT.

7.8.1.8 COVID-19 related analyses

The subgroup of patients with SARS-COV-2 infection will be analysed. SARS-COV-2 infections will be defined by the narrow BIcMQ SARS-COV-2 infection. All analyses will be repeated using the broad instead of the narrow BIcMQ.

An overview of adverse events will be presented for this subgroup of patients. Additionally, the number of patients with adverse events, the number of serious AEs and AEs leading to discontinuation of study treatment will be presented by treatment, primary SOC and PT.

A listing will be prepared presenting all SARS-COV-2 infections.

7.8.2 **Laboratory data**

For continuous safety laboratory parameters, standardised and normalised values will be derived as well as the differences to baseline. The process of standardisation and normalisation as well as standard analyses for safety laboratory data are described in the BI guidance for the “Handling, Display and Analysis of Laboratory Data” (8). All analyses considering multiple of times ULN will be based on original and not normalised data.

The frequency of the number of patients with AST/ALT elevations $\geq 3\times$ ULN, $\geq 5\times$ ULN, $\geq 10\times$ ULN, and $\geq 20\times$ ULN will be displayed.

To support analyses of liver related adverse drug effects, patients with AST and/or ALT $\geq 3\times$ ULN with concomitant or subsequent TBILI $\geq 2\times$ ULN in a 30 day period after AST/ALT elevation are of special interest.

The start of the 30 day time span is triggered by each liver enzyme elevation above the defined thresholds. Patients who fulfil one or two of the criteria for ALT/AST or total bilirubin elevations above and has no information available for the remaining parameter(s) at the same time-point or within the 30 day time window will not be listed under “ALT and/or AST $\geq 3\times$ ULN with Total Bilirubin $\geq 2\times$ ULN”.

Patients with elevations as described will be summarised and stratified by Alkaline phosphatase $< 2\times$ ULN and $\geq 2\times$ ULN.

All calculations for the grading of renal function will be based on the originally measured laboratory values and the ULNs given by the laboratory, not on normalised values with BI standard reference ranges. The glomerular filtration rate will be estimated according to the MDRD formula (please see [Table 6.4: 1](#)) and stored in the trial databases.

For the analysis of eGFR and for the covariates in the statistical modelling, the values calculated by the MDRD formula using the serum creatinine values from the central laboratory will be used, not the eGFR values provided by the central laboratory. For the assignment of iPDs based on renal function the central laboratory values will be used.

To support analysis of renal function, eGFR throughout the trial will be categorised according to the MDRD staging shown in [Table 7.8.2: 1](#).

Table 7.8.2: 1 MDRD staging

Stage	eGFR [mL/min/1.73m²]	Description
1	≥ 90	Normal renal function
2	60 to < 90	Mild renal impairment
3A	45 to < 60	Moderate renal impairment A
3B	< 45	Moderate renal impairment B to end-stage renal impairment

The analyses of laboratory data will be descriptive in nature and will be based on BI standards (see DM&SM: “Handling, Display and Analysis of Laboratory Data”) (8).

Baseline for safety laboratory parameters will be the last available measurement before the start of randomised trial medication. Laboratory measurements taken up to 3 days after the last administration of randomised trial medication will be considered as on-treatment.

Laboratory values will be compared to their reference ranges and frequency tables will be provided for the number of patients within and outside the reference range at baseline and the last measurement on treatment. Descriptive statistics will be provided by treatment group for baseline, on-treatment values and for changes from baseline. Frequency tables will summarise the number of patients with potentially clinically significant abnormalities. Details on patients with elevated liver enzymes will be listed. Summaries will also be presented for patients with elevated liver enzymes.

A summary will also be created representing the number of patients per treatment group that experienced a doubling in creatinine on treatment compared to baseline that was out of the normal range.

Only patients with at least one available on-treatment value will be included in the analysis of an individual laboratory parameter. All individual data will be presented in listings.

A shift table from baseline to last value on treatment for eGFR using MDRD formula will also be provided.

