5.2.3 Safety laboratory parameters

Safety laboratory parameters to be assessed are listed in Table [5.2.3: 1](#), [5.2.3: 2](#) and [5.2.3: 3](#). For the sampling time points please see the flowchart.

All analyses will be performed by a central laboratory, the respective reference ranges will be provided in the ISF.

Safety laboratory samples (except screening) will be collected after a full overnight fast (nothing to eat or drink except water for at least 10 hours) and before administration of background antidiabetic therapies and investigational drug as described in the flowchart and [Section 6](#). The blood sample at Visit 1 (screening visit) can be taken with the patient in a fasted or nonfasted state.

Instructions regarding sample collection, sample handling/ processing and sample shipping are provided in the ISF (lab manual).

It is the responsibility of the investigator to evaluate the laboratory reports. Clinically relevant abnormal findings as judged by the investigator will be reported as AE (please refer to Section [5.2.6](#)).

In case the criteria for hepatic injury are fulfilled, a number of additional measures will be performed (see Section [5.2.6.1](#) and the DILI checklist provided in the ISF). The amount of blood taken from the patient concerned will be increased due to this additional sampling.

The central laboratory will transfer the results of the analysis to the sponsor.

Table 5.2.3: 1

Safety laboratory tests – Haematology

Visit	1	2	3	4	5	6	7	8 EOT	9 EOS
Study week	-3	-2	0	4	12	24	36	52	53*
Haematocrit	X		X	X	X		X	X	X
Haemoglobin	X		X	X	X		X	X	X
Red Blood Cells (RBC)/Erythrocytes	X		X	X	X		X	X	X
WBC/Leukocytes	X							X	
Platelet Count/Thrombocytes	X							X	
Differential Automatic (relative and absolute count): Neutrophils, Eosinophils, Basophils, Monocytes, Lymphocytes	X							X	

* EOS should be done 1 week after Visit 8 or EOT

Table 5.2.3: 2

Safety laboratory parameters – Clinical Chemistry

Visit	1	2	3	4	5	6	7	8 EOT	9 EOS
Study week	-3	-2	0	4	12	24	36	52	53*
Glucose (fasted)	X	X	X	X	X		X	X	X
Lipase	X		X	X	X		X	X	X
AST (aspartate transaminase, SGOT)	X		X	X	X		X	X	X
ALT (alanine transaminase, SGPT)	X		X	X	X		X	X	X
Alkaline phosphatase	X		X	X	X		X	X	X
Bilirubin total	X		X	X	X		X	X	X
Direct bilirubin, if bilirubin total increased	X		X	X	X		X	X	X
Total Protein	X		X	X	X		X	X	X
Albumin	X		X	X	X		X	X	X
Potassium	X		X	X	X		X	X	X
Sodium	X		X	X	X		X	X	X
Bicarbonate	X		X	X	X		X	X	X
Creatinine	X		X	X	X		X	X	X

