Blood urea nitrogen	X		X	X	X		X	X	X
Calcium	X		X						X
Inorganic phosphorous			X						X
Uric acid	X		X						X
Cholesterol (total)			X						X
HDL cholesterol			X						X
LDL cholesterol			X						X
Triglycerides			X						X
Thyroid stimulation hormone	X								

* EOS should be done 1 week after Visit 8 or EOT

Table 5.2.3: 3

Safety laboratory parameters – urine

Visit	1	2	3	4	5	6	7	8 EOT	9 EOS
Study week	-3	-2	0	4	12	24	36	52	53*
Protein	X		X	X	X		X	X	X
Ketone	X		X	X	X		X	X	X
Leucocytes	X		X	X	X		X	X	X
Erythrocytes	X		X	X	X		X	X	X

* EOS should be done 1 week after Visit 8 or EOT

If the investigator needs safety lab (e.g., to follow an ongoing AE), he/she can perform it in the local lab. The results will not be captured in the eCRF. Clinically significant lab abnormalities will be reported as AE (see Section [5.2.6](#)).

Estimate glomerular filtration rate

The estimated glomerular filtration rate (eGFR) will be derived from serum creatinine* values based on the standard MDRD formula:

$$\text{eGFR (ml/min/1.73 m}^2\text{)} = 175 \times [\text{Screatinine (umol/L)/88.4}]^{-1.154} \times [\text{age}]^{-0.203} \times [0.742 \text{ if patient is female}] \times [1.212 \text{ if patient is of African origin}]$$

*: creatinine methods calibrated to an IDMS reference method

NT-proBNP will be measured at screening as part of baseline examinations to characterise the patient population in the trial.

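### Seven chemistry analytes, including the cholesterol measures, are sampled after randomisation only at Visit 9, outside the SAP's 3-day on-treatment window, so their planned laboratory tables would be empty

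*SAP*

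**What the plan says.** **Schedule.** Protocol Table 5.2.3:2 (clinical chemistry) has nine visit columns. Calcium and uric acid are marked at Visits 1, 3 and 9. Inorganic phosphorus, total, HDL and LDL cholesterol and triglycerides are marked at Visits 3 and 9. The table footnote fixes Visit 9: "EOS should be done 1 week after Visit 8 or EOT". Protocol 6.2.3 places it 7 days after the last dose, with a window that only runs later, by up to 7 days.

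**On-treatment window.** SAP 7.8.2 states: "Laboratory measurements taken up to 3 days after the last administration of randomised trial medication will be considered as on-treatment". SAP Table 6.7:1 gives the same 3 days. SAP 6.7 treats Visit 3 values as baseline and anything after the window as post-treatment.

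**Inclusion rule and outputs.** SAP 7.8.2 admits a patient to a parameter's analysis only under this condition: "Only patients with at least one available on-treatment value will be included in the analysis of an individual laboratory parameter". It promises that "frequency tables will be provided for the number of patients within and outside the reference range at baseline and the last measurement on treatment". It also plans descriptive statistics for baseline, on-treatment values and changes from baseline, and frequency tables of potentially clinically significant abnormalities. Finally, "All individual data will be presented in listings".

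**The concern.** Each rule is reasonable alone, but for these seven analytes they do not fit together. The schedule collects the only follow-up value after treatment has ended. The SAP then summarises only patients who have a value from during treatment or within 3 days of its end.

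What is lost is the tabulated comparison between arms. Protocol 7.2.5 commits to quantitative and qualitative laboratory analysis with the groups compared descriptively, and it exempts no analyte. Protocol 1.4.2 reports slightly raised total, LDL and HDL cholesterol with empagliflozin. A 52-week placebo-controlled trial would thus collect lipids and tabulate no comparison of them. For the other four analytes the protocol names no increase (for triglycerides it reports no significant change), but the same rule removes them.

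**Working it through.** The plan gives no figure to reproduce here. The check sets the schedule against the window.

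**1. Which analytes lack an on-treatment sample (Protocol Table 5.2.3:2, nine cells per row)**

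| Rows | Visits marked | Any of Visits 4 to 8? |
|---|---|---|
| Calcium, uric acid (2) | 1, 3, 9 | No |
| Inorganic phosphorus, total, HDL and LDL cholesterol, triglycerides (5) | 3, 9 | No |
| Glucose to blood urea nitrogen (14) | include 4, 5, 7, 8, 9 | Yes |
| Thyroid stimulating hormone (1) | 1 | Not sampled after randomisation |

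Analytes sampled after randomisation: 2 + 5 + 14 = 21. Without any sample at Visits 4 to 8: 2 + 5 = 7, which is one third of the 21.

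**2. When Visit 9 falls relative to the last dose**

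- Completers (Protocol 6.2.3): 7 + 0 to 7 + 7, so day 7 to day 14.
- Early stop, follow-up declined (Protocol 6.2.2 and flow-chart footnote 2): the EOT visit is 0 to 7 days after stopping and EOS 7 days after that. 0 + 7 to 7 + 7 gives day 7 to day 14.
- Early stop, follow-up continued to Week 53: weeks off drug = 53 − week of stopping. Stopping at Week 4, 24 or 36 gives 49, 29 or 17 weeks.

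**3. Comparison with the window**

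The limit is day 3 and the earliest scheduled Visit 9 sample is day 7. For completers the sample misses the window by 7 − 3 = 4 days at best and 14 − 3 = 11 days at worst. The number of scheduled on-treatment values per patient is 0 for each of the seven analytes, so 0 of about 128 patients qualify for their tables.

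**4. Could a value come from elsewhere?**

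Visit 3 values are baseline. Protocol 5.2.3 allows additional local safety tests but keeps their results out of the eCRF. That leaves only an off-schedule central sample or a Visit 9 held earlier than the protocol allows.

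**5. Would a wider window solve it?**

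A 7-day limit would catch only Visit 9 samples taken exactly on day 7. It would take 14 days to cover every completer, and that would call values on-treatment after the 7-day residual effect period in Protocol 1.2 has passed.

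**6. Comparison within the protocol**

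In Table 5.2.3:1 (haematology) the tests done once after randomisation, namely leukocytes, "Platelet Count/Thrombocytes" and the differential, are marked at Visit 8, not Visit 9. They yield an on-treatment value in completers.

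**The case against.** **The column may be misread.** The finding turns on whether a mark sits under Visit 8 or Visit 9. The protocol is available here as converted text, the flow-chart grid is not shown, and Protocol 5.2.3 refers to that flow chart for sampling times. A complete set of nine cells does not rule out a mark shifted by one column. This stands as a caveat. Against it, all seven rows agree with one another, and the neighbouring haematology table clearly separates Visit 8 from Visit 9.

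**Visit 9 may be intended.** SAP 7.8.4 schedules the ECG at Visits 3 and 9, so a baseline-plus-EOS pattern does occur in this trial. Intent would explain the schedule, but it would not make the SAP's tables usable for these analytes.

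**Other text may cover the values.** SAP 7.8.2 cites a sponsor guidance document that is not available here, and Protocol 7.2.5 says in general terms that safety data at the end-of-trial evaluation will be assessed for change. Neither displaces the explicit 3-day limit and inclusion rule. SAP 7.8.2 itself describes no post-treatment laboratory summary.

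**The stakes are limited.** This is correct. None of the seven is a primary or secondary endpoint, a laboratory criterion for an adverse event of special interest, or one of the parameters the SAP plots over time. Safety analysis is descriptive, and all values are still listed. Creatinine, electrolytes, liver tests and haematocrit are sampled at Visit 8 and are unaffected.

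**Conclusion.** The concern holds on the documents as printed. For 7 of 21 chemistry analytes, the schedule and the SAP's inclusion rule together leave 0 of about 128 patients in the planned tables. The day 7 to 14 timing for completers is enough to establish this; the longer gaps for early discontinuers only add to it.

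The conclusion rests on two assumptions: that the column positions are as printed, and that Visit 9 is held within its protocol window. Confidence is medium because of the first. The reach is confined to descriptive safety tables, with no effect on the primary analysis or on the main renal, hepatic and haematological summaries. It should still be corrected, because as written the plan promises tables that its own schedule cannot fill, including those for cholesterol, where the protocol reports a drug effect.

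**What to change.** 1. **Check the source.** Compare the seven rows with the original Table 5.2.3:2 and the flow chart. If the marks belong under Visit 8, correct the table.

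2. **If Visit 9 is confirmed and sampling can still change,** assay the seven analytes on the chemistry sample already drawn at Visit 8/EOT, instead of or in addition to Visit 9. Fasting is already required there: "Safety laboratory samples (except screening) will be collected after a full overnight fast". The cost is seven assays and an edit to the protocol table and lab manual, with no extra visit or venepuncture. One limit remains: EOT may be up to 7 days after an early stop, so samples drawn on days 4 to 7 would still miss the window. The gain is mainly in completers.

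3. **If sampling can no longer change,** state in SAP 7.8.2 that for these seven analytes the change from baseline to Visit 9 is summarised separately by arm and labelled post-treatment, with treatment completers shown apart from early discontinuers. The separation matters because discontinuers may have been off drug for months. The cost is one or two sentences.

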7.8.3 Vital signs

Vital signs (SBP, DBP and pulse rate) will be taken at Screening (Visit 1) through EOT (Visit 8). Only descriptive statistics are planned for the summary of vital signs for baseline, on-treatment and change from baseline by visit. Descriptive statistics will also be shown graphically for SBP and DBP.

7.8.4 ECG

12-lead ECG measurements will be taken at baseline (Visit 3) and EOS (Visit 9). ECG-findings before first intake of trial medication will be considered as baseline condition. Any clinically significant new findings in the ECG measurement after the first ECG will be considered as AEs and analysed as planned in [Section 7.8.1](#).

7.8.5 Others

Time curve analysis

Descriptive statistics will be presented in tables for creatinine, eGFR, haematocrit, haemoglobin and weight over time by treatment. Presented values will be used to create plots of the parameters over time.

In addition, tables of descriptive statistics for creatinine, eGFR values will also be presented for age subgroups.

Secondary endpoints analyses

Secondary endpoints in this trial only provide one post-baseline assessment (no repeated measurements). ANCOVA will be performed to compare the change from baseline in each of the continuous secondary endpoints at week 52 on the TS (OC-IR).

The statistical model will be: Change from baseline in secondary endpoint after 52 weeks = baseline secondary endpoint + age + sex + treatment + BMI + baseline HbA1c + random error.

In addition, descriptive statistics will be provided by visit including actual values and change from baseline values in the abovementioned secondary endpoints at Week 52. Descriptive statistics will also be presented with boxplots in each group both at baseline and at Week 52.

8. TIMEPOINT OF RELEASE OF TREATMENT INFORMATION

The treatment information will be released to unblind the trial database after the last patient has completed their End-of-Study/Follow-up visit and all data has been entered and cleaned as defined in the “Data Ready to be Unblinded and/or Final Trial Closure Notification” (RUN) form.

